## 6.1 Schedule of Events

Procedure:	Visit:	SCREENING (Windows outlined in Section 6.2)	CYCLE 1	CYCLES 2 AND BEYOND (WITHIN 72 HRS PRIOR)	END OF TREATMENT (WITHIN 14 DAYS OF LAST STUDY DRUG ADMINISTRATION)	FOLLOW UP (28 +/- 7 DAYS AFTER LAST DOSE OF TREATMENT)	SURVIVAL FOLLOW UP EVERY 90 +/- 14 DAYS AFTER LAST DOSE
Informed Consent		X					
Medical History, Demographic Information		X					
Clinical Exam		X	X	X	X		
Performance status (PS) 		X	X	X	X		
Vital Signs (VS) including height  , weight, and BSA 		X	X	X	X		
Numbered Pain Rating Scale 			X	X	X		
Labs (CBC diff, CMP) 		X	WEEKLY 	X			X 
Pregnancy Test (Urine or Serum) 		X	X	X			
INR		X					
Tibial x-ray 		X		X 			
Provide Study Drug for home administration			X	X			
Tumor disease evaluation 		X		EVERY 2 CYCLES 	X		
Tumor NGS 		X					
Circulating tumor DNA (ctDNA) 				X	X		
Provide and/or Review Subject Diary			X	X	X		
Concomitant Medication Review 		X	X	X	X		
Adverse Event Review 			X	X	X	X	
Survival Assessment							X

Abbreviations: VS=vital signs (blood pressure, temperature, pulse and respiratory rates, weight and height); CBC/diff=complete blood count and white blood cell differential; CMP = complete metabolic profile (sodium, potassium, chloride, bicarbonate, blood urea nitrogen, creatinine, glucose, alkaline phosphatase, AST, ALT, total bilirubin, protein), NGS Next Generation Sequencing

1 Performance status: Pediatric Karnofsky for subjects  $\geq$  16 years of age and Lansky for subjects 12-15 years of age; Adult ECOG score (18+)

UF-SC-001

2024-Aug-12

- 2 Numbered Pain Rating Scale , refer to Appendix G.
- 3 Laboratory tests at baseline need not be repeated if therapy starts within 72 hours of obtaining labs to assess eligibility. Labs are to be collected weekly for Cycle 1 (Days 1, 8, 15, and 22) +/- 72 hours. If patients have Grade 4 neutropenia then CBCs should be checked at least every other day until recovery to Grade 3 or until meeting the criteria for dose limiting toxicity. Automated differentials acceptable unless concern for blasts; then please obtain manual differential.
- 4 Female subjects of childbearing potential only.

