- 5 Patients must have either CT or MRI of primary and metastatic tumors, as well as whole body 18F-FDG PET/CT. Radiographic Tumor Assessment using RECIST 1.1 criteria. Imaging to be obtained every 2 cycles +/- 7 days from Cycle 1 Day 1 until disease progression or death. Screening imaging studies must be obtained within 30 days prior to start of protocol therapy.
- 6 Tumor NGS will be sent as part of standard of care, if not already done. If already done, results will be recorded as part of medical history review.
- 7 Circulating tumor DNA (ctDNA) results will be collected whenever obtained per standard of care.
- 8 Height and BSA only collected for pediatric subjects.
- 9 Adverse events, comed collection, and all sample collections, should be performed pre-dose at every cycle. The study drug will be provided at study visits, but self-administered at home throughout the trial. Cycles may be repeated for up to a total duration of therapy of 2 years (maximum 26 cycles), provided the patient meets the criteria for starting subsequent cycles and does not meet any of the criteria for removal from protocol therapy criteria.
- 10 Only to be completed for subjects <18 years of age. Screening tibial x-ray may have been performed within the past 6 months (180 days) before treatment (C1D1).
- 11 Tibial x-rays to be completed every 180 +/- 30 days only for those with open growth plates at screening.
- 12 CBC only – at each survival follow-up visit for five years, then yearly (at least once per calendar year) up to 10 years. Once a subject begins new anti-cancer therapy, they will be followed for survival only.

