#### 6.4 Follow up/ Evaluations

Subjects will have a follow-up visit for the evaluation of adverse events 28 days ( $\pm$  7 days) after the last dose of study medication. Any adverse events ongoing at the follow up visit will be followed until resolution or start of a new therapy. If the subject is unavailable to travel to the institution, the visit may be made via telephone interview to review for adverse event resolution or the occurrence of any new adverse events. Additionally, external or internal medical records may be consulted with permission of the subject to complete remote visit reporting.

Subjects will continue to be contacted via telephone for survival approximately every 90 +/- 14 days until death. Safety labs (CBC) will be performed as part of these visits for 5 years, then annually until 10 years (at least once per calendar year) after last dose of therapy. Labs may be collected at an outside laboratory as standard of care. If study therapy is discontinued for reasons other than progression, continue imaging/disease assessments per standard of care until progression or until start of another therapy or death. Following discontinuation of study therapy for any reason, report the date the first non-protocol anti-cancer therapy is administered. Once a subject begins new anti-cancer therapy, the subject will be followed for survival only.

If a subject becomes unreachable during the course of the study, the investigator or study team will make a reasonable effort to contact the subject and document each attempt (in accordance with Section 4.3.4 of the ICH E-6 GCP). If these attempts are not successful, the subject may be declared "lost to follow up." For subjects lost to follow-up, the termination date will be the date of last contact with the subject.

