#### 10.1.6 Special Warnings and Precautions for Use

Secondary Malignancies: TAZVERIK increases the risk of developing secondary malignancies, including T-cell lymphoblastic lymphoma, myelodysplastic syndrome, and acute myeloid leukemia.

Embryo-Fetal Toxicity: Can cause fetal harm. Advise subjects of potential risk to a fetus and to use effective non-hormonal contraception.

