#### 11.4.2 Other Events Requiring Immediate Reporting

All pregnancies, regardless of outcome, must be reported to the UFHCC CRO Project Management Office (PMO; [[contact]](mailto:[contact])), including pregnancies that occur in the female partner of a male study subject. All pregnancies must be followed to outcome. Pregnancies and follow-ups will be submitted by PMO to DISC, the sponsor if required, and any other regulatory authorities required.

Although overdose and cancer are not always serious by regulatory definition, these events should also be reported to the UFHCC CRO Project Management Office (PMO; [[contact]](mailto:[contact])) in an expedited manner. In case the overdose did not result in any adverse event, the Investigator should report this as "overdose, no adverse event" and provide the intended amount, as well as the actual amount, of drug administered. In the event of overdose or exaggerated response, appropriate supportive measures should be employed. Actual treatment should depend on the severity of the clinical situation and the judgment and experience of the treating physician. Overdose events and follow-ups will be submitted by PMO to DISC, the study sponsor if required, and any other regulatory

authorities required.

Pregnancies and overdoses should be documented and reported per the reporting guidelines below.

Institution Immediate Reporting Information
SAEs and pregnancies must be reported to the UFHCC CRO Project Management Office (PMO), or assigned designee at:  Email: [contact] As well as entered in OnCore, the study CTMS.

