**Appendix A: PROTOCOL VERSION HISTORY / SUMMARY OF CHANGES**

Protocol Version Number	Protocol Version Date	Affected Section(s)	Summary of Revisions Made
1.0	June 15, 2021	N/A- Initial protocol	
1.1	August 6, 2021	Added Epizyme reporting information and email; Removed repeated exclusion criteria (inclusion I)	
1.2	September 22, 2021	Clarified amount of time between screening and baseline procedures needing to be repeated; Added language regarding abnormal lab values as AEs; Added clarifying language to appendix E so study team can use a comparable drug accountability log.	
1.3	January 10, 2022	Removed Phos, Mag, and Uric Acid from labs to be done at each cycle and weekly for cycle 1. Removed ECG and urinalysis from screening and eligibility criteria (exclusion D). Modified inclusion criteria D to include washout period for prior myelosuppressive chemotherapy. Clarified section 3.1 ctDNA testing to be collected whenever obtained per SOC.	
1.4	May 3, 2022	Added tibial x-rays for pediatric subjects. Added surveillance CBCs with every surveillance visit until 5 years, then yearly until 10 years. Expanded screening visit windows to accommodate subject schedules and standard of care. Changed wording of "physical" exam to "clinical" exam. Removed research blood section 9.1 as it was not being collected per protocol before but there was one sentence not removed.	
1.5	October 27, 2023	Sample Size Justification  Interim Analysis for Efficacy  Exclusion Criteria  Section 11.4.3	Changed statistical design from Simon's two-stage Minimax to Simon's two-stage Optimum.  Clarified Exclusion Criteria A and D Added Exclusion Criteria J and K.  Updated safety reporting email address.
1.6	December 8, 2023	Section 6.1  Section 6.4  Section 6.2	Clarified that subjects who begin new anti-cancer therapy while in follow up will be followed for survival only.  Added 72 hour window for weekly labs.
1.7	August 12, 2024	Section 6.2	Corrected typo in the Allowable Visit Window Table, which was previously IRB approved with Protocol v1.6.

UF-SC-001

2024-Aug-12

	Exclusion Criteria	Added B-cell acute lymphoblastic leukemia (B-ALL) to exclusionary medical history in Exclusion Criteria C, per sponsor request.
--	---------------------------	---

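### The 90-day survival calls carry no listed question on new malignancy, so after new anti-cancer therapy starts, T-LBL, MDS and AML are reportable but not asked about: a cheap improvement

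*Combined protocol and SAP*

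**What the plan says.** - **The risk.** Section 10.1.6 says the drug "increases the risk of developing secondary malignancies, including T-cell lymphoblastic lymphoma, myelodysplastic syndrome, and acute myeloid leukemia".
- **The schedule.** The last column of the section 6.1 table, headed "SURVIVAL FOLLOW UP EVERY 90 +/- 14 DAYS AFTER LAST DOSE", marks two items: labs, which footnote 12 limits to a CBC, and the survival assessment. Adverse event review is last marked at the 28-day visit.
- **How long.** Section 6.4: "Subjects will continue to be contacted via telephone for survival approximately every 90 +/- 14 days until death". The CBCs run at each contact for five years and then yearly to ten.
- **What changes with new therapy.** Footnote 12: "Once a subject begins new anti-cancer therapy, they will be followed for survival only". Section 6.4 says the same. The only related item collected is in 6.4, which tells sites to "report the date the first non-protocol anti-cancer therapy is administered".
- **History.** Appendix A shows that both steps were deliberate. Version 1.4: "Added surveillance CBCs with every surveillance visit until 5 years, then yearly until 10 years". Version 1.6: "Clarified that subjects who begin new anti-cancer therapy while in follow up will be followed for survival only".
- **Reporting duties that remain.** Section 11.4.2: "Although overdose and cancer are not always serious by regulatory definition, these events should also be reported" in an expedited manner, with no causality test and no time limit. Section 11.2 asks the investigator to notify the DISC of SAEs after day 30 that are believed to be drug-related. Section 11.3.1 counts a known side effect of the drug as related.

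**The concern.** The plan treats blood malignancy as a long-term drug risk: it names the risk, excludes subjects with such histories, and follows counts for ten years in a trial that enrolls from age 12. Yet the one active check ends when new anti-cancer therapy starts, and nothing asked at the continuing calls takes its place. A subject who is later treated elsewhere and found to have MDS or AML is telephoned to establish whether he or she is alive. The study learns of the diagnosis only if someone volunteers it.

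At stake is the completeness of a short list of serious cases. A trial of 9, 29 or at most 50 subjects cannot estimate this risk, so the aim is to miss no case. The primary endpoint is not involved.

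**Working it through.** There is no plan figure to reproduce here. The check is a reading of the text, followed by a count of the calls that the added question would use.

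**1. What is scheduled, and what is only reportable, by period**

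| Period | Scheduled collection bearing on new malignancy | Duty to report if known |
|---|---|---|
| To day 30 after last dose | All SAEs (11.2); adverse event review at the 28-day visit (6.1) | Same, plus 11.4.2 |
| After day 30, before new therapy | CBC at each 90-day contact for 5 years, then yearly to 10; no malignancy question | 11.4.2; 11.2 with 11.3.1 |
| After new therapy | Survival status only | 11.4.2; 11.2 with 11.3.1 |

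If new therapy starts before the 30-day visit, 11.2 still collects SAEs to day 30 and keeps adverse events that are possibly related or clinically significant. All 90-day contacts fall after that window. The third row is where unsolicited reporting stands alone.

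**2. Is a late case reportable?** Yes, by two routes. Section 11.4.2 makes cancer reportable whatever its cause. Separately, T-LBL, MDS or AML would normally meet the SAE definition in 11.1.2. Section 10.1.6 makes them known drug risks, 11.3.1 lets a known side effect be classed as related, and 11.2 then covers them with no end date. Neither route is tied to a scheduled question.

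**3. How many calls would carry the question?**

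Inputs:
- MPNST chemotherapy series (section 1.2): median PFS 17 weeks, median OS 48 weeks.
- Epithelioid sarcoma on tazemetostat (section 1.4.2): median PFS 5.5 months, median OS 19 months.
- Call spacing d = 90 days, with a window of 76 to 104 (section 6.1).
- Cap C = 24 months, or 730.5 days, of participation (section 3.1), or no cap (6.4, until death).

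Assumptions: the last dose falls at progression, and both the time to progression and the time from last dose to death are exponential and independent.

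Mean time to last dose, μ1 = median PFS / ln 2:
- MPNST: 17 / 0.6931 = 24.5 weeks = 172 days.
- Epithelioid sarcoma: 5.5 / 0.6931 = 7.9 months = 242 days.

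Mean time from last dose to death, μ2 = (median OS − median PFS) / ln 2:
- MPNST: (48 − 17) / 0.6931 = 44.7 weeks = 313 days.
- Epithelioid sarcoma: (19 − 5.5) / 0.6931 = 19.5 months = 593 days.

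Expected calls per subject with no cap = 1 / (exp(d/μ2) − 1).

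Expected calls with cap C = the sum over k = 1, 2, … with kd < C of exp(−kd/μ2) × [1 − exp(−(C − kd)/μ1)].

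| | MPNST medians | Epithelioid sarcoma medians |
|---|---|---|
| Until death, d = 90 | 3.00 | 6.10 |
| Until death, d = 76 / 104 | 3.64 / 2.54 | 7.31 / 5.21 |
| 24-month cap, d = 90 | 2.32 | 3.10 |
| 24-month cap, d = 76 / 104 | 2.83 / 1.95 | 3.76 / 2.62 |

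At 90-day spacing the range is about 2 to 6 calls per subject. These are all survival calls, before and after new therapy. They measure the cost of the question, not the number of cases missed. Splitting them at new therapy would need an uptake rate, which the documents do not give.

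**The case against.** The strongest reply is that the duty to report already exists twice over, so the issue is solicited against unsolicited collection of events that are already reportable. That stands, and it rules out the stronger reading that a reader might infer, namely that late leukemias fall outside the trial's safety system. They do not.

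Three further points also stand.
- Before new therapy, the CBCs are active surveillance, though partial. Treatment for a leukemia would normally itself be new anti-cancer therapy, whose start date 6.4 already collects. That catches a first treated case, but not one arising after other therapy has begun, because only the first start date is asked for.
- A reader might think the safety analysis discards late cases. Section 12.6 excludes only non-serious events more than 30 days after the last dose.
- Ending blood draws after new therapy was deliberate and is defensible, since later findings are confounded by that therapy. The same confounding limits what any late case can show about the drug.

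The CRFs, data management plan, procedure manual and contract were not available and may already contain the question. Section 14.8 does not settle it. It ties CRFs to protocol-required outcomes: no question is listed, but cancer is a required report.

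What the reply does not remove is that a reporting duty works only on what is known. Neither amendment entry gives a reason for not asking on a call that takes place anyway.

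**Conclusion.** The point holds as a cheap improvement to safety ascertainment. Once new anti-cancer therapy starts, the protocol lists nothing that asks about the malignancies it names as drug risks, although contact continues. Cases remain reportable; their capture is unsolicited and may be incomplete.

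The number of cases affected cannot be stated. The documents give no incidence, latency or uptake of later therapy, and they do not support any claim that cases will be missed in a given number. ORR, alpha and power are unaffected.

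The only figure is the cost: about 2 to 6 calls per subject. The lower end uses the MPNST medians with the 24-month participation in section 3.1; the upper end uses the epithelioid sarcoma medians with calls until death. The MPNST medians come from chemo-naive patients, so survival here may be shorter and the count lower. The conclusion is limited to what the protocol lists.

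**What to change.** In section 6.1 footnote 12 and section 6.4, keep the survival-only rule for procedures and add: *At each survival contact, including after new anti-cancer therapy, ask for and record any new T-LBL/T-ALL, B-ALL, MDS, AML, MPN or other second malignancy, with diagnosis date and intervening therapy.* Report positive answers under 11.4.2. List the cases descriptively, with intervening therapy and without attribution to the drug. A cross-reference from 11.2 to 11.4.2 is optional.

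The cost is one question on a call already made and a few CRF fields: event yes/no, diagnosis, date, and intervening therapy. The therapy field goes beyond 6.4, which now takes only the date of the first new therapy. No visit, test or change to the sample size is needed. If the CRF already asks, the amendment only brings the protocol into line.

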## 6.2 Allowable Visit Windows

Visit Name	Window
Screening	
Informed Consent	≤ 28 days prior to Cycle1 Day 1 (C1D1)
Medical History, Physical examination, Performance Status, Concomitant Medications, and Labs (CBC Diff, CMP, INR, pregnancy test)	≤ 28 days prior to Cycle1 Day 1 (C1D1)
Tibial X-Ray	≤ 180 days prior to Cycle1 Day 1 (C1D1)
Imaging (CT and PET)	≤ 30 days prior to Cycle1 Day 1 (C1D1)
All other screening procedures	≤ 7 days prior to C1D1
Cycle 1 Day 1	
Labs	Laboratory tests at screening need not be repeated if therapy starts within 72 hours of obtaining labs to assess eligibility. All others to be done ≤ 72 hours of C1D1 dosing. Labs are to be collected weekly for Cycle 1 (Days 1, 8, 15, and 22) +/- 72 hours
All other baseline procedures (which include complete physical exam, performance status, vital signs, and concomitant medication review)	Baseline procedures completed at screening need not be repeated if therapy starts within 72 hours of performing procedures to assess eligibility. All others to be done ≤ 72 hours of C1D1 dosing.
Day 1 of subsequent cycles (after Cycle 1)	
Assessments	Within 72 hours prior to dosing
Study treatment administration (dosing)	Every 28 days
Tibial X-Ray	Every 180 +/- 30 days
Tumor Assessments	Imaging every 2 cycles +/- 7 days from Cycle 1 Day 1 until disease progression or death.
End of Treatment (EOT) Procedures	Within 14 days of last dose of therapy
28-Day Safety Follow-up	28 +/- 7 days after last dose of treatment

Survival Follow-Up	Every 90 +/- 14 days
--------------------	----------------------

#### 6.3 End of Treatment Evaluations

The end of treatment visit as well as evaluations will occur within 14 days following the last dose of therapy. End of treatment evaluations will also be performed within 14 days if the subject is discontinued as per section 8.2.

#### 6.4 Follow up/ Evaluations

Subjects will have a follow-up visit for the evaluation of adverse events 28 days ( $\pm$  7 days) after the last dose of study medication. Any adverse events ongoing at the follow up visit will be followed until resolution or start of a new therapy. If the subject is unavailable to travel to the institution, the visit may be made via telephone interview to review for adverse event resolution or the occurrence of any new adverse events. Additionally, external or internal medical records may be consulted with permission of the subject to complete remote visit reporting.

Subjects will continue to be contacted via telephone for survival approximately every 90 +/- 14 days until death. Safety labs (CBC) will be performed as part of these visits for 5 years, then annually until 10 years (at least once per calendar year) after last dose of therapy. Labs may be collected at an outside laboratory as standard of care. If study therapy is discontinued for reasons other than progression, continue imaging/disease assessments per standard of care until progression or until start of another therapy or death. Following discontinuation of study therapy for any reason, report the date the first non-protocol anti-cancer therapy is administered. Once a subject begins new anti-cancer therapy, the subject will be followed for survival only.

If a subject becomes unreachable during the course of the study, the investigator or study team will make a reasonable effort to contact the subject and document each attempt (in accordance with Section 4.3.4 of the ICH E-6 GCP). If these attempts are not successful, the subject may be declared "lost to follow up." For subjects lost to follow-up, the termination date will be the date of last contact with the subject.

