- Women of childbearing potential (WOCBP) who are heterosexually active must be using two highly effective methods of contraception to avoid pregnancy throughout the study and for at least 6 months after the last dose of study drug to minimize the risk of pregnancy as Tazemetostat might counteract the effects of hormonal contraceptives. Birth control methods that can be used while in this study include: established use of oral, injected or implanted hormonal birth control or placement of an intrauterine device [IUD] or intrauterine system [IUS]. They or their partner must also use a second method, (e.g., condom with spermicidal foam/gel/film/cream/suppository or occlusive cap [diaphragm or cervical/vault caps] with spermicidal foam/gel/film/cream/suppository. If their male partner is vasectomized, they do not need to use any of the birth control methods listed above. The type of birth control they use must be discussed with the study doctor before beginning the study. The study doctor must approve the method you use before they can enter the study. Prior to study enrollment, women of childbearing potential must be advised of the importance of avoiding pregnancy during trial participation and the potential risk factors for an unintentional pregnancy.
- Males with female partners of child-bearing potential must agree to use physician-approved contraceptive methods (e.g., abstinence, condoms, vasectomy) throughout the study and should avoid donating sperm, for 90 days following the last dose of study drug.

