#### 4.3 Exclusion Criteria

Subjects with any of the following present at time of enrollment will not be eligible for study participation:

- A. Subjects who are currently taking the following concomitant medications:
  - Anti-cancer Agents: Subjects who are currently receiving other anti-cancer agents are not eligible.
  - CYP3A4 Agents: Subjects who are currently receiving drugs that are strong inducers or strong inhibitors of CYP3A4 are not eligible. Strong inducers or inhibitors of CYP3A4 are prohibited from 14 days prior to the first dose of Tazemetostat to the end of the study. Note: Dexamethasone for CNS tumors or metastases, on a stable dose, is allowed.
  - Grapefruit, grapefruit juice, Seville oranges and food/drinks containing them should be avoided one week before the first dose of the study intervention
- B. Subjects who are acutely ill with an uncontrolled active infection on systemic anti-infective agents are not eligible.

- C. Subjects with a prior history of T-LBL/T-ALL, myelodysplastic syndrome (MDS), acute myeloid leukemia (AML), B-cell acute lymphoblastic leukemia (B-ALL), or other myeloproliferative neoplasm (MPN).
- D. Subjects who have any of the following underlying major cardiac issues or conditions:
  - Known QTc prolongation or documentation
  - Documented New York Heart Association (NYHA) Class III or IV congestive heart failure.
  - Myocardial infarction within 6 months prior to registration.
  - Unstable angina within 6 months prior to registration.
  - Symptomatic arrhythmia.
- E. Subjects who in the opinion of the investigator may be high risk for treatment complications or unable to comply with the safety monitoring requirements of the study are not eligible.
- F. Heterosexually active males or females of reproductive potential may not participate unless they have agreed to use two highly effective contraceptive methods for the duration of study treatment as Tazemetostat might counteract the effects of hormonal contraceptives. Female subjects of childbearing potential should agree to remain abstinent or use adequate contraceptive methods for 6 months after the last dose of Tazemetostat. Male subjects should agree to remain abstinent or use adequate contraceptive methods, and agree to refrain from donating sperm, and for 90 days after the last dose of Tazemetostat.

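### After the last adverse event review, 21 to 35 days post-dose, no scheduled contact covers pregnancy, although contraception runs 6 months (women) or 90 days (men) and all pregnancies must be reported

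*Combined protocol and SAP*

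**What the plan says.** **Risk and window.** Section 10.1.6 warns that the drug "Can cause fetal harm". Section 4.3 G adds that no human fetal or teratogenic data are available at present. Section 4.2 J requires women of childbearing potential who are heterosexually active to use contraception "throughout the study and for at least 6 months after the last dose of study drug to minimize the risk of pregnancy". For men, section 4.3 F asks for abstinence or contraception and that they "agree to refrain from donating sperm, and for 90 days after the last dose of Tazemetostat".

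**Reporting duty.** Section 11.4.2 states: "All pregnancies, regardless of outcome, must be reported to the UFHCC CRO Project Management Office". It extends this to female partners of male subjects, requires follow-up to outcome and sets no end date. Section 8.2 applies the timelines used for serious adverse events.

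**Scheduled collection.**
- The pregnancy-test row in section 6.1 is marked at Screening, Cycle 1 and Cycles 2 and beyond. It is blank at End of Treatment, Follow Up and Survival Follow Up. It applies to female subjects of childbearing potential only.
- Adverse event review is last marked at the visit 28 +/- 7 days after the last dose. Section 11.2 ends routine adverse event collection at 30 days.
- Section 6.4 then says: "Subjects will continue to be contacted via telephone for survival approximately every 90 +/- 14 days until death". The other items it lists are a blood count, standard-of-care imaging for subjects who stopped without progression, and the date of the first new anti-cancer therapy. Once such therapy starts, follow-up is for survival only.

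**The concern.** The protocol defines a period after dosing in which conception is to be avoided, and it wants every pregnancy reported and followed. The visit schedule has no procedure that would bring most of that period to the study team's notice. From the last adverse event review onward, a pregnancy is recorded only if the subject happens to mention it. For partners of male subjects, the protocol text contains no scheduled question at any time, on or off treatment.

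At stake is the completeness of one kind of safety information, in a setting where the protocol itself says human data are lacking. A pregnancy that nobody reports cannot be followed to outcome, so the duty in 11.4.2 would go unmet without anyone having departed from the schedule.

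**Working it through.** The plan states no figure on this point, so there is none to reproduce. The check is day-count arithmetic.

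**Inputs**
- Women's window W: at least 6 months (4.2 J), taken as 183 days; 180 days as a check.
- Men's window W: 90 days (4.2 J, 4.3 F), read as covering contraception as well as sperm donation.
- Last adverse event review d: day 21 to 35 (28 +/- 7; 6.1, 6.2, 6.4).
- Survival calls: every 90 +/- 14 days after the last dose (6.1, 6.4).
- Last scheduled pregnancy test: within 72 hours before Day 1 of the last cycle started (6.1).

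**Step 1. Share of the post-dose window after the last adverse event review, (W - d)/W**

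| Group | d = 35 | d = 21 |
|---|---|---|
| Women, W = 183 | 148/183 = 80.9% | 162/183 = 88.5% |
| Women, W = 180 | 145/180 = 80.6% | 159/180 = 88.3% |
| Men, W = 90 | 55/90 = 61.1% | 69/90 = 76.7% |

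This counts a general adverse event review as coverage of pregnancy. That is generous to the plan, because the definition in 11.1.1 does not mention pregnancy. If only a pregnancy-specific test or question counts, scheduled coverage of the post-dose window is nil in both sexes. For women, up to 28 days of the last cycle then also follow the last test, or fewer if treatment stops mid-cycle.

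**Step 2. What the share becomes if treatment time T is added, (W - d)/(T + W)**
- T = 119 days (17 weeks, the first-line median PFS cited in section 1.2, used only as an illustration). Women: 148/302 to 162/302 = 49-54%. Men: 55/209 to 69/209 = 26-33%.
- T = 728 days (26 cycles of 28 days, the maximum). Women: 148/911 to 162/911 = 16-18%. Men: 55/818 to 69/818 = 7-8%.
- The share drops below one half once T exceeds W - 2d. Women: 183 - 70 = 113 to 183 - 42 = 141 days. Men: 90 - 70 = 20 to 90 - 42 = 48 days.

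For men, this step treats on-treatment adverse event review as coverage of partner pregnancy, although no partner question is scheduled.

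**Step 3. What the existing calls could reach**
- First call: day 76 to 104. At its earliest it reaches 76/90 = 84% of the men's window.
- Second call: day 166 to 194. At its earliest it reaches 166/183 = 91% of the women's window.
- So those two calls alone need not close either window. The call after each does. For men, the second call is at least 166 - 90 = 76 days past the window. For women, the third call (day 256 to 284) is at least 256 - 183 = 73 days past it.

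**The case against.** The strongest reply is that the duty to report does not lapse. Section 11.4.2 has no end date. A congenital anomaly is a serious adverse event under 11.1.2, and 11.2 asks the investigator to notify the safety committee of related serious events after day 30. It also keeps possibly related or clinically significant events in scope once new therapy starts. Passive reporting and a schedule with no later question do not contradict each other, so active questioning is a design preference. Within the first weeks, 11.1.1 tells staff to probe for adverse events at each visit. The case report forms and Data Management Plan are not in the documents, and the consent pages were removed from the text reviewed, so instructions there cannot be checked. The trial is small: 29 evaluable subjects, up to 50 accrued.

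Much of this stands. A reader might infer that pregnancy ascertainment ends at the last cycle. The documents do not support that: scheduled testing ends, while the reporting duty continues and becomes passive. A reader might also infer that most exposed pregnancies would be missed. That does not follow either. The percentages count days, the documents give no conception rate, and pregnancies conceived on treatment are exposed too. Step 2 shows how far the share of time falls when treatment is included.

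What the reply does not remove is that, in the protocol text, no scheduled contact after day 35 covers pregnancy and no visit asks about partners.

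**Conclusion.** The gap is real and modest. No scheduled contact covers pregnancy for about 81-89% of the women's post-dose contraception window and 61-77% of the men's, and for that time 11.4.2 relies on spontaneous report. The figures rest on 6 months being 183 days, on the last adverse event review falling on day 21 to 35, and on counting that review as coverage. They are shares of window time. The number of pregnancies or subjects affected cannot be derived.

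The absence of a partner question is a statement about the protocol text only. The length of the contraception periods is not judged. The primary endpoint, sample size and type I error are untouched. This is an inexpensive improvement to safety collection that serves a duty the protocol already imposes.

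**What to change.** - In 6.1 and 6.4, add a scripted question on pregnancy in the subject or partner since the last contact. Put it at the End of Treatment visit, the 28-day follow-up and the survival calls at about 90 and 180 days.
- Make the closing question the next scheduled call after each window: about 180 days for men and about 270 days for women. The calls may fall as early as day 76 or day 166, and late conceptions may not yet be recognised.
- Ask it even if new anti-cancer therapy has started, and handle any positive answer under 11.4.2.
- Do not put a pregnancy end date into 11.2, since that could narrow an open-ended duty. State there that the 30-day adverse event limit does not restrict pregnancy reporting under 11.4.2, and reconcile 6.1, 6.4, 11.2 and 11.4.2.

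Cost: one question and one case report form field at contacts already scheduled, plus the wording changes. No new visit, procedure or staff is needed.
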